1.2.2. Pharmacokinetics of NTZ in Humans

NTZ is not detectable in the plasma following oral administration of the drug. The main metabolites of NTZ in humans are tizoxanide and tizoxanide glucuronide. Tizoxanide is highly bound to plasma proteins (>99%). The absorption of NTZ in immediate release tablets is significantly enhanced (C_{max} and AUC of tizoxanide and tizoxanide glucuronide in plasma are more than doubled) when it is administered with food. In fasted human volunteers receiving a single 500 mg dose of ¹⁴C NTZ, approximately one-third of the dose was excreted in urine as tizoxanide and tizoxanide glucuronide, and two-thirds was excreted in feces as tizoxanide. No other significant metabolites were detected. (Investigators Brochure for NTZ 300 mg Tablets, July 2018)

The pharmacokinetics of tizoxanide and tizoxanide glucuronide during repeated oral dosing of nitazoxanide (NTZ) 300 mg extended release tablets administered 600 mg twice daily with food were evaluated in healthy volunteers. Twelve (12) subjects received two NTZ controlled release tablets twice daily with food for 7 days. The pharmacokinetics were studied in plasma up to 12 hours post-dose after the morning dose on Day 1 and Day 7, and before the morning dose on Day 2-6. Based on mixed effect analysis of variance, the steady state tizoxanide and tizoxanide glucuronide plasma

concentrations was reached by Day 2, after one day of treatment with NTZ at 600 mg b.i.d. The main pharmacokinetics parameters of tizoxanide and tizoxanide glucuronide are summarized in the table below:

Table 1: Summary of Tizoxanide and Tizoxanide Glucuronide Pharmacokinetics Parameters

PK Parameter (unit)	Tizoxanide		Tizoxanide Glucuronide	
	Day 1 N=12	Day 7 N=12	Day 1 N=12	Day 7 N=12
C _{max} (μg/mL)	5.23 ± 2.71	8.16 ± 4.16	4.88 ± 1.72	8.96 ± 3.48
t _{max} (h)	6.00 (4.00-9.00)	5.00 (3.00-8.00)	6.00 (5.00-11.00)	5.50 (0.00-7.02)
t _{lag} (h)	0.00 (0.00-2.00)	0.00 (0.00-0.00)	0.50 (0.00-2.00)	0.00 (0.00-0.00)
AUC _{0-t} (μg.h/mL)	26.9 ± 16.1	52.5 ± 33.7	29.5 ± 12.1	75.0 ± 37.8
AUC _{0-∞} (μg.h/mL)	28.6 ± 16.3 ^a	48.3 ± 31.9 ^b	30.5 ± 12.2 ^c	75.2 ± 37.9
C _T (μg/mL)	0.709 ± 0.987	1.72 ± 2.04	1.39 ± 0.846	3.89 ± 2.88
AUC _{0-∞} (μg.h/mL)	27.8 ± 17.8 ^b	52.3 ± 35.6 ^b	35.3 ± 16.5 ^d	62.1 ± 24.2 ^e
t _{1/2} (h)	1.66 ± 0.408 ^b	2.19 ± 0.485 ^b	2.70 ± 0.848 ^c	4.99 ± 5.20
λ _z (1/h)	0.441 ± 0.106 ^b	0.331 ± 0.0733 ^b	0.282 ± 0.0902 ^c	0.201 ± 0.0813
C _{avg} (μg/mL)	NA	4.02 ± 2.66 ^b	NA	6.27 ± 3.16

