### 11.2. Primary Efficacy Analysis: Time to Symptom Response

The primary efficacy analysis will be the comparison of the time from first dose of study medication to Symptom Response between treatment groups using Kaplan-Meier survival curves and a Gehan-Wilcoxon test stratified by (1) time from onset of illness to time of first dose of study medication (0-24, >24-≤36, or >36 hours from onset), (2) pre-enrollment use of symptom relief medication, and (3) presence of underlying lung condition including asthma, COPD, or past or present history of smoking. Separate Symptom Response definitions will be determined for ITTI subjects with no underlying lung condition and for ITTI subjects with underlying lung conditions. Time to Symptom Response will be calculated in the same way for the two groups and all ITTI subjects will be analyzed together.

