#### Analysis

Plasma concentrations of T and TG will be summarized descriptively for both treatment groups. Exploratory analyses will be conducted to evaluate relationships between plasma concentrations and age, race, gender, body weight, body mass index, concomitant medications (yes/no), changes in viral titer over time, Time to Symptom Response, and adverse events (yes/no). For continuous factors, the relationship with plasma concentrations will be assessed by Spearman's correlation analysis and Pearson's correlation analysis. For categorical factors, plasma concentrations will be compared among groups using the Kruskal-Wallis test.

Analysis Population(s): ITTI, NTZ-treated only

Derived Variables: Concomitant medication use: if any concomitant medication is used, then "yes", otherwise "no"

Adverse events: if any adverse event is reported, then "yes", otherwise "no"

Changes in viral titer over time: see [Section 11.5.5](#)

Time to Symptom Response: see [Section 11.2](#)

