### 11.6.2. Analysis of Time to Symptom Response by Symptom Relief Medication Use for Placebo-Treated Subjects

Repeat the primary efficacy analysis for the ITTI and ITT populations comparing placebo-treated subjects who did not use symptom relief medication to placebo-treated subjects who did use symptom relief medication. Sum of baseline FLU-PRO symptom assessments (<42 or  $\geq$ 42) will be included as a factor in the analysis. Pre-enrollment symptom relief medication use will not be used as a factor in the analysis since the groups being compared are classified by symptom relief medication use.

Analysis Population(s): ITTI placebo-treated subjects, ITT placebo-treated subjects

Derived Variables: See Section 11.2: Primary Efficacy Analysis

**11.6.3. Analysis of Time to Ability to Perform All Normal Activities by Symptom Relief Medication Use for Placebo-Treated Subjects**

Repeat the analysis of time to ability to perform all normal activities for the ITTI and ITT populations comparing placebo-treated subjects who did not use symptom relief medication to placebo-treated subjects who did use symptom relief medication. Sum of baseline FLU-PRO symptom assessments ( $<42$  or  $\geq 42$ ) will be included as a factor in the analysis. Pre-enrollment symptom relief medication use will not be used as a factor in the analysis since the groups being compared are classified by symptom relief medication use.

Analysis Population(s): ITTI placebo-treated subjects, ITT placebo-treated subjects

Derived Variables: See Section 11.4.1 Time to Ability to Perform All Normal Activities

**11.6.4. Proportion of Subjects Experiencing Complications of Colds by Symptom Relief Medication Use for Placebo-Treated Subjects**

Repeat the analysis of proportion of subjects experiencing complications of colds for the ITTI and ITT populations comparing placebo-treated subjects who did not use symptom relief medication to placebo-treated subjects who did use symptom relief medication using a Fisher's exact test.

Analysis Population(s): ITTI placebo-treated subjects, ITT placebo-treated subjects

Derived Variables: None

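### SAP 11.6.1 tests exposure-response in the NTZ arm only by one-factor correlations, which adjust for nothing and have no rule for censored response times; its viral titer cross-reference is also wrong (minor).

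*SAP*

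**What the plan says.** SAP Section 11.6.1 sets out the analysis of Day 3 tizoxanide and tizoxanide glucuronide levels. The population line reads "Analysis Population(s): ITTI, NTZ-treated only". The factors are age, race, gender, weight, BMI, concomitant medication, titer change, Time to Symptom Response and adverse events. The wording runs from the last three factors into the method: "changes in viral titer over time, Time to Symptom Response, and adverse events (yes/no). For continuous factors, the relationship with plasma concentrations will be assessed", naming Spearman and Pearson correlation. The other rule is "For categorical factors, plasma concentrations will be compared among groups using the Kruskal-Wallis test". No strata or covariates are named, and Protocol Section 8.4.2 adds none. Age, weight and the other demographic factors appear only as separate correlates of concentration.

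Two pointers sit under Derived Variables. The one for Time to Symptom Response goes to Section 11.2. Given where it sits, it supplies the variable and not the stratified test. The other, "Changes in viral titer over time: see", goes to Section 11.5.5, which compares proportions with detectable virus. Change in log titer is defined in 11.5.4.

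Three other places matter:
- Section 11.2.2 censors subjects without a response at their last symptom assessment.
- Section 11.2 says "Separate Symptom Response definitions will be determined for ITTI subjects with no underlying lung condition and for ITTI subjects with underlying lung conditions", and the primary test is stratified by lung condition.
- Sections 11.6.2 and 11.6.3, which compare non-randomized groups of placebo subjects, include as a factor "Sum of baseline FLU-PRO symptom assessments", split at 42.

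Protocol Section 2 and SAP Section 8.1 both list the relationship between pharmacokinetics and clinical or virologic response among the other important objectives.

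**The concern.** Randomization protects the comparison of NTZ with placebo. It does not protect a comparison of high and low concentrations within the NTZ arm. Anything that affects both the Day 3 level and the course of the illness can produce a correlation with no drug effect behind it, and 11.6.1 has no analysis that could separate the two.

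The response variable raises a separate problem. Time to Symptom Response can be censored, and a correlation coefficient has no place for a censored value. If the censored time is entered as though it were the response time, a subject who stops the diary early without recovering looks like a fast responder. If such subjects are dropped, the slowest recoveries are lost selectively. The SAP does not say which would be done.

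The cross-reference slip would lead a programmer who follows it to a yes/no variable where a change in log titer is meant.

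At stake is the answer to a stated, though exploratory, objective. A correlation of higher level with faster recovery would invite reading as evidence of a drug effect.

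**Working it through.** **The plan's own figures.** Section 11.6.1 states no sample size, power or error rate, so it offers nothing to reproduce. The nearest figure is the trial's size in SAP Section 8.3: 530 / (1 − 0.12) = 602.3, or 603, against the stated 600. That agrees closely enough to use 300 per arm.

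**Inputs from the documents**
- Sampled NTZ subjects: at least 75% are expected at the Day 2 and 3 visits (SAP 8.2), so 0.75 × 300 = 225. With the 700 maximum, 0.75 × 350 ≈ 262. This assumes that the 75% applies equally to infected NTZ subjects.
- Day 3 trough tizoxanide CV: 101% (Protocol Table 2), giving a log-scale SD of √ln(1 + 1.01²) = 0.84.
- End of follow-up: 504 hours. Tests are two-sided at 5%.

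**Assumed, because the documents give no values**
- Baseline severity correlates −0.1 to −0.3 with log concentration and +0.3 or +0.5 with log recovery time.
- Lung condition is present in 30% of subjects. It lowers log concentration by 0 to 0.5 SD and, where included, lengthens log time by 0.5 SD.
- Recovery time is log-normal with median exp(5.3) ≈ 200 hours and log SD 0.7, capped at 504 hours.

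**Simulation.** There were 4,000 runs per scenario, with concentration having no effect on recovery. The table shows false-positive rates at n = 225.

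| Scenario | Mean Spearman | Spearman | Pearson |
|---|---|---|---|
| Severity and lung condition affect time, not concentration | 0.00 | 5.0% | 5.2% |
| Severity −0.1 / +0.3 | −0.03 | 7.2% | 5.9% |
| Severity −0.2 / +0.3 | −0.06 | 13.8% | 10.8% |
| Severity −0.3 / +0.3 | −0.09 | 25.1% | 19.1% |
| Severity −0.3 / +0.5 | −0.14 | 57.2% | 45.0% |
| Lung only, 0.25 SD lower concentration | −0.02 | 6.3% | 5.3% |
| Lung only, 0.5 SD lower concentration | −0.05 | 10.8% | 7.3% |
| Severity −0.2 / +0.3, lung 0.25 SD | −0.08 | 20.9% | 16.2% |
| Severity −0.3 / +0.3, lung 0.5 SD | −0.13 | 49.6% | 35.5% |

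At n = 262 the Spearman rate runs from 4.8% to 65.3%.

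**Hand check of the severity rows.** With a single common cause, the induced correlation is the product of the two paths. For −0.3 / +0.3 it is −0.09. The matching Spearman value is (6/π)·arcsin(−0.09/2) = −0.086. Its approximate rejection rate is Φ(0.086 × √224 − 1.96) + Φ(−0.086 × √224 − 1.96) = Φ(−0.67) + Φ(−3.25) ≈ 25.1%. The same steps give 7.1%, 13.8% and 57.4% for the other three severity rows.

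**Adjusted analysis.** A partial Spearman correlation, adjusted for severity and lung condition, rejects in 4.2% to 5.7% of runs across all scenarios and both sample sizes. This is the best case, because it adjusts for the exact confounders that were generated.

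**Censoring.** The simulation caps times at 504 hours and has no early dropout, so it does not measure this part. As a guide to scale, 12% incomplete data among 225 is 27 subjects. Protocol Table 7 shows 29 of 115 NTZ subjects (25%) censored for return to normal activities in RM08-3002. The sample size section takes that study's placebo curve for the endpoint as its proxy. Its diary schedule differed, so the 25% is only indicative.

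**The case against.** The strongest reply is that this is an exploratory analysis outside the tested hierarchy of Section 11.4, that no decision rule depends on it, and that the size of the problem comes from assumed inputs. All of that stands. The spurious correlations are also small on average, at most about 0.14 in absolute size, and the clean result after adjustment holds partly by construction. In the trial, the baseline FLU-PRO sum is only a proxy for severity.

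Some stronger readings are tempting, and the documents do not support them.

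- *That pooling two response definitions creates the link by itself.* It does not. In the scenario where lung condition lengthens recovery but is unrelated to concentration, the rate is 5.0%. Protocol Section 3 presents the two definitions, each anchored to return to usual health, as the way to analyze all subjects together. Lung condition also has no part in defining titer change, so for virologic response the argument rests on severity.
- *That the food effect shows sicker subjects have lower levels.* Protocol Section 1.2.2 reports the effect for immediate-release tablets, whereas it and Section 3 describe the NTZ 300 mg tablet as extended release. Protocol Sections 5.2 and 9.1 require food with every dose. Meal size may still vary, but a path from illness through appetite to trough level is conjecture.
- *That the SAP adjusts its non-randomized comparisons everywhere except here.* Sections 11.6.2 and 11.6.3 do, but 11.6.4 uses an unadjusted Fisher's exact test. They show that the adjustment is feasible. They do not establish a practice that 11.6.1 breaks.

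The reply does not remove three things: the within-arm comparison is unprotected by randomization, the response time can be censored, and the titer pointer is wrong.

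**Conclusion.** The point holds as a minor one. Section 11.6.1 cannot distinguish an effect of concentration from confounding by baseline severity or other prognostic factors, and it has no rule for censored response times. Its titer variable is cross-referenced to the wrong section.

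Whether a spurious link would actually appear is unknown, because it needs a factor associated with both concentration and recovery. Under the assumptions shown, the Spearman false-positive rate is 5% with no association with concentration, about 25% with modest confounding, and 50% or more with strong confounding. These figures are a range over assumptions and do not estimate the bias in this trial. The censoring and cross-reference points follow from the text alone. Nothing here affects the primary or secondary conclusions.

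**What to change.** In SAP Section 11.6.1:

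1. Keep the correlations and the Kruskal-Wallis comparisons as descriptive. State that they are unadjusted and that concentration is not randomized.
2. Add a time-to-event model, for example Cox, of Time to Symptom Response on log concentration, for tizoxanide and tizoxanide glucuronide separately. Stratify by or adjust for lung condition. Enter baseline FLU-PRO sum, onset-to-dose time, pre-enrollment symptom relief medication, age and weight as covariates. Censor as in Section 11.2.2.
3. Add a linear regression of change in log titer on log concentration, adjusted for baseline log titer, onset-to-dose time and baseline FLU-PRO sum.
4. Change the titer cross-reference from 11.5.5 to 11.5.4.

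Covariates are preferable to fully crossing the randomization factors. That would give 3 × 2 × 2 = 12 strata, or about 225 / 12 ≈ 19 subjects each on average. The latest onset stratum could be sparse, since entry is capped at 40 hours and the stratum starts after 36.

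The cost is SAP wording, some code and a few degrees of freedom. The covariates are already collected. Residual confounding would remain, and the report should say so.

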8.4.1. Efficacy Analyses

Efficacy analyses will be based on a population consisting of all subjects that received at least one dose of study drug and had laboratory-documented EV/RV infection (infected intent-to-treat or ITTI population). Laboratory-documented EV/RV infection is defined by identification of EV/RV in nasopharyngeal secretions by RT-PCR at baseline, Day 2 or Day 3. For time to event analyses a test of significance (as described in the following) will be performed with descriptive statistics provided including the use of Kaplan-Meier figures.

There will be one primary efficacy analysis:

- Time to Symptom Response for the NTZ treatment group will be compared to that of the placebo treatment group using a stratified Gehan-Wilcoxon test ($\alpha = 0.05$) where stratification will follow that used for randomization. Subjects without a Symptom Response being recorded will be treated as censored as of their last diary without a documented Symptom Response.

If the primary analysis is significant at the 0.05 level, a key secondary efficacy analysis will be formally evaluated at the 0.05 level as follows:

- Time to Ability to Perform All Normal Activities for the two treatment groups will be compared using a stratified Gehan-Wilcoxon test ($\alpha = 0.05$) where stratification will follow that used for randomization. Subjects without an Ability to Perform All Normal Activities response being recorded will be treated as censored as of their last diary without a documented Ability to Perform All Normal Activities response.

If both the primary analysis and the key secondary efficacy analysis are significant at the 0.05 level, another secondary efficacy analysis will be formally evaluated at the 0.05 level as follows:

- Proportions of subjects experiencing one or more complications of colds due to EV/RV infection will be compared between the treatment groups using a Cochran-Mantel-Haenszel test stratified by the randomization strata ($\alpha = 0.05$).

Exploratory analyses will be performed as follows:

- For each of the 32 individual FLU-PRO symptoms, Time to Individual Symptom Response for the NTZ and placebo treatment groups will be compared using the Gehan-Wilcoxon test.
- For each of the 6 FLU-PRO domains, Time to FLU-PRO Domain Response for the NTZ and placebo treatment groups will be compared using the Gehan-Wilcoxon test.

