### 8.3. Sample Size Justification

The Symptom Response definitions for this study will be derived from the subjects' FLU-PRO questionnaire responses as described in [Section 11.2.1](#). The FLU-PRO-derived endpoint is expected to track very closely to return to usual health status (a daily yes/no question in the FLU-PRO questionnaire), which in turn is expected to track very closely to ability to perform 100% of normal activities. We assume, therefore, that the cumulative distributions of time to Symptom Response for the placebo treatment group will closely reflect historical data from Romark Study RM08-3002 for time from first dose until the EV/RV-infected subjects report that they are able to perform 100% of usual activities (see placebo curve in chart below). Then, to calculate sample size, we assume that treatment with NTZ treatment should result in reduction of at least 48 hours in median time to symptom response. The following curves have been developed for determining sample size.

Based upon these curves, a sample size of 530 subjects with laboratory-confirmed EV/RV infection (i.e. 265 for each of the 2 groups) will provide 90% power to detect a statistically significant difference in the survival distributions between the NTZ and placebo groups (2-sided  $\alpha=0.05$ ). This calculation was performed for the Gehan rank test using SAS PROC POWER (SAS 9.4) with the curves shown above (proportion not recovering by the end of each day was used as input) and censoring at Day 21 (hour 504). Assuming that up to 12% of subjects will have incomplete data, we arrive at a sample size of 600 subjects in total, 300 per treatment group to yield at least approximately 530 with complete data (all EV/RV-infected subjects who receive at least one dose of study medication will be included in the primary analysis with subjects with incomplete data censored as of their last entry).

Based upon these calculations, the study will enroll at least 600 subjects with laboratory-confirmed EV/RV infection up to a maximum of 700 subjects with laboratory-confirmed EV/RV infection.

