#### **11.2.2. Analysis of the Primary Efficacy Parameter**

The primary efficacy parameter, time to Symptom Response, will be derived as follows:

Event: Time of Symptom Response – time of the first dose

Censored: Time of last symptom assessment – time of the first dose

If Symptom Response is achieved at the time of the first symptom assessment diary record, the subject will be excluded from the analysis.

If Symptom Response is not achieved prior to a subject’s last available diary assessment, but the criteria are met at the last available diary assessment with no evidence of symptom relief medication intake during that diary period, time of Symptom Response will be considered to have occurred at the start of the last daily diary period.

Time to Symptom Response for the NTZ treatment group will be compared to that of the placebo treatment group using a Gehan-Wilcoxon test stratified by (1) time from onset of illness to time of first dose of study medication (0-24, >24-≤36, or >36 hours from onset), (2) pre-enrollment use of symptom relief medication, and (3) presence of underlying lung condition including asthma, COPD, or past or present history of smoking. The comparison will be graphically depicted using Kaplan-Meier curves.

Analysis Population(s): ITTI

Derived Variables: Event: Time of Symptom Response – time of first dose

Censored: Time of last symptom assessment – time of first dose

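### SAP 11.6.1 correlates Day 3 plasma concentration with a right-censored time by Spearman and Pearson and gives no rule for censored subjects (minor)

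*SAP*

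**What the plan says.** SAP 11.6.1 announces the analysis so: "Exploratory analyses will be conducted to evaluate relationships between plasma concentrations and age, race, gender". The list goes on to body size, concomitant medication, change in viral titer, Time to Symptom Response and adverse events. The method depends on the type of factor: "For continuous factors, the relationship with plasma concentrations will be assessed by" Spearman and Pearson correlation, with Kruskal-Wallis for categorical factors. The analysis set is "ITTI, NTZ-treated only".

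Time to Symptom Response is taken by reference from SAP 11.2. In 11.2.2 it has two forms, one for events and one for subjects without a response: "Censored: Time of last symptom assessment – time of the first dose". Protocol 8.4.1 agrees: "Subjects without a Symptom Response being recorded will be treated as censored as of their last diary". SAP 11.6.1 adds no censoring indicator and no rule for subjects who carry the censored form. Protocol 8.4.2 plans the same comparison without naming a method.

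Elsewhere the SAP keeps a survival method for this endpoint. The sensitivity analyses (11.3), the ITT and virus-subgroup analyses (11.5.6, 11.5.9), the onset-time subgroups (11.5.10 to 11.5.12) and the placebo-only analysis (11.6.2) all repeat the primary analysis or follow 11.2.2.

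Protocol 2 and SAP 8.1 list the relationship between pharmacokinetics and clinical or virologic response among the other important objectives.

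**The concern.** A programmer following 11.6.1 has to choose between two unsuitable routes.

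- **Enter the censoring time as if it were a recovery time.** A subject whose diary stops at 96 h without a response then ranks ahead of most true responders. In the historical NTZ data for normal activities the lower quartile was 109 h (Protocol Table 7). Subjects still unwell at hour 504 are scored as recovering then.
- **Leave censored subjects out.** This removes the slowest recoveries, which carry much of the information about a concentration effect.

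Under the first route, drop-out that is commoner at high concentration produces short recorded times at high concentration, which reads as benefit. The documents offer a possible mechanism: gastrointestinal effects increased with dose (Protocol 3), and a severe adverse reaction leads to withdrawal from the study (Protocol 10.4). At stake is the credibility of the exposure-response statement in the study report.

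**Working it through.** **Inputs from the documents**

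- Size: 530 subjects, up to 12% incomplete (SAP 8.3). 530/(1 − 0.12) = 602.3, so 603, against the stated 600. Conversely 600 × 0.88 = 528. The plan's figure is reproduced approximately.
- Subjects with a Day 3 sample: at least 75% (SAP 8.2), so 0.75 × 300 = 225 on NTZ.
- End of follow-up: "censoring at Day 21 (hour 504") in SAP 8.3.
- Historical NTZ times (Protocol Table 7): median 189.5 h, quartiles 109 and 402 h. As a lognormal, the SD of log time is ln(402/109)/1.349 = 0.967. The share beyond 504 h is then 1 − Φ(ln(504/189.5)/0.967) = 1 − Φ(1.01), about 16%.
- Historical NTZ censoring: 29/115 = 25% for normal activities (Table 7) and 6/116 = 5% for symptom alleviation (Table 5).
- Day 3 tizoxanide trough: mean 2.36 µg/mL, CV 101% (Protocol Table 2). The SD of log concentration is √ln(1 + 1.01²) = 0.84.

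**Assumptions, not in the documents:** the shape of the time distribution, when drop-out occurs, its odds ratio per SD of log concentration (OR), and the true effect. The documents state no power or error rate for this analysis.

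**Base setting.** Lognormal times, drop-out uniform over 60-504 h, n = 225, 1,500 simulated data sets, two-sided 5%. With 12% drop-out, 18.5% of times are censored. About 4.8 points come from drop-out before response, because many who stop have already responded. Spearman and Pearson use the censoring time as observed. Cox is the score test on log concentration.

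| True effect | Drop-out | OR | Spearman | Pearson | Cox |
|---|---|---|---|---|---|
| none | 12% | 1 | 5.3% | 5.4% | 5.3% |
| none | 12% | 1.5 | 5.7% | 4.9% | 5.1% |
| none | 12% | 2 | 5.2% | 6.9% | 5.5% |
| none | 12% | 3 | 6.8% | 7.5% | 4.7% |
| none | 25% | 2 | 9.1% | 7.8% | 4.4% |
| none | 25% | 3 | 13.1% | 14.4% | 4.1% |
| −0.2 log time per SD | 0% | – | 82.7% | 69.6% | 78.7% |
| −0.2 | 12% | 1 | 79.1% | 66.9% | 78.8% |
| −0.2 | 12% | 0.5 | 69.2% | 55.4% | 79.4% |

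Monte Carlo error is √(0.05 × 0.95/1500) = 0.6 points near 5% and about 1 point near 80%.

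**Earlier drop-out and another time distribution.** The alternative is exponential times with median 250 h and follow-up of 485 h, so 0.5^(485/250) = 26% are unresolved at the end before any drop-out. Here n is 230 to 240 and drop-out is 12%.

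- No true effect, OR 2.2, drop-out packed into 48-240 h: Spearman 12-14% (lognormal) and 15-16% (exponential).
- No true effect, OR 2.2, drop-out spread over follow-up: Spearman about 7-9%.
- No true effect, OR 1.5, early drop-out, exponential: 8%.
- Over the full set of settings at n = 230: about 5% with independent drop-out, 5-9% at OR 1.5 and 8-19% at OR 2.2, against 4-6% for Cox. Single runs at 7% agree with the lower end within simulation error.
- True effect, independent drop-out, exponential: Spearman 67.4%, Cox 80.2%, a gap of 12.8 points. The base setting shows no gap, hence 0-13 points.
- True effect, drop-out commoner at low concentration (OR 0.45): Spearman 30-74%, Cox 78-87%.

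**Censored subjects left out.** Spearman power falls to 51% in the base setting at 12% drop-out (Pearson 39%), against 78.8% for Cox. With exponential times it falls to 18%. With lognormal times and a slightly larger effect (0.22) it is a little over 60%.

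**The case against.** The strongest reply is that little depends on this. The analysis sits under other exploratory analyses, uses NTZ-treated subjects only and lies outside the testing hierarchy of SAP 11.4. Historically fewer than 1% of subjects stopped therapy for an adverse event (Protocol 1.2.6), so strong exposure-related drop-out is not demonstrated. The allowance of up to 12% is for incomplete data, not for drop-out before response, and SAP 11.2.2 counts a response met only at the last diary as an event. All of this stands and limits the severity.

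Three stronger readings are tempting and are not supported.

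- **That the SAP treats censored times as observed.** It is the natural reading of the reference to 11.2, but 11.6.1 does not say so. Leaving those subjects out is equally open.
- **That about one analysis in five would show a false association.** One run at an unfavourable corner gave 19.8% for Spearman and 22.2% for Pearson. It needs OR 2.2, exponential times and all drop-out before 240 h. Repeats of nominally the same setting gave 15-16% and 18%. Relaxing either the odds or the timing brought both to 8-9%.
- **That censoring explains Pearson's low power.** Much of the deficit comes from skewed raw concentrations. Pearson is already at 69.6% with no drop-out. In the exponential setting, taking logs raises it from 59% to 72%.

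None of this supplies a rule for censored subjects or makes the coefficients suitable for a censored time.

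**Conclusion.** The point holds and is minor. SAP 11.6.1 assigns two coefficients that cannot represent censoring to a right-censored time and leaves the handling of censored subjects open. If censoring times are used as observed, the type I error is sound when drop-out is unrelated to concentration and inflated when it is not. The inflation is modest at odds 1.5 and clear at odds 2.2 when drop-out is early. The loss of power ranges from nothing to 13 points under independent drop-out, and is greater when drop-out is commoner at low concentration. Excluding censored subjects costs most, leaving about 18-60% power against 79-87%.

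These sizes rest on assumed dependence, drop-out timing, effect and time distribution. Exponential proportional hazards favours Cox, and the lognormal fit to the sponsor's own quartiles gives the smaller differences. A reader might infer that the efficacy result is at risk. It is not: the primary and secondary comparisons do not use this analysis.

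**What to change.** In SAP 11.6.1, for Time to Symptom Response only, replace both correlations with a Cox model stratified by the randomization strata. Use the event/censored coding of 11.2.2 and log concentration as the covariate, with tizoxanide and tizoxanide glucuronide in separate models. Keep the correlations for the uncensored continuous factors.

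The cost is one sentence and one additional model, with no new data and no change to the sample size or the testing order.
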